APPENDIX 3 REVISED PROTOCOL SUMMARY OF CHANGE HISTORY

[figure not shown]
Overall Rationale for the Revised Protocol 02b, 30-May-2019

[figure not shown]
The below changes are due to a DMC recommendation to increase oversight of patients at the initiation of the infusion.

SUMMARY OF KEY CHANGES FOR REVISED PROTOCOL 02B		
Section Number & Title	Description of Change	Brief Rationale
Table 5.1-2: Treatment and In-Hospital Follow-up (CV013011)	Additional Blood Pressure and Heart Rate Measurements at: 15 minutes, 45 minutes, and 1.5 hours.	
Section 5.3.1: Assessment of Blood Pressure and Symptoms for Hypotension	Clarification that blood pressure measurements within ± 5 min in the first hour, then ± 15 min of the specified timepoints in Table 5.1-2.	

Overall Rationale for the Revised Protocol 02a, 13-Mar-2019

These changes serve to clarify the milestone, timing of enrollment and inclusion/exclusion criteria of the Japanese population. While the enrollment in the main study protocol will continue until 210 patients have been randomized globally in Part II (Cohort 2), enrollment in Japan may continue further only in Japan until approximately 18 total Japanese subjects are randomized.

SUMMARY OF KEY CHANGES FOR REVISED PROTOCOL 02A		
Section Number & Title	Description of Change	Brief Rationale
Section 3.1: Study Design and Duration; Synopsis	Section modified to add: while the enrollment in the main study protocol will continue until 210 patients have been randomized globally in Part II (Cohort 2), enrollment in Japan may continue further only in Japan until approximately 18 total Japanese subjects are randomized.	

SUMMARY OF KEY CHANGES FOR REVISED PROTOCOL 02A		
Section Number & Title	Description of Change	Brief Rationale
Section 3.3.1: Inclusion Criteria; Synopsis	Inclusion criteria # 2G) was modified to decrease the minimum allowable BNP levels from ≥ 400 pg/mL (116 pmol/L) to ≥ 350 pg/mL (101 pmol/L) and NT-proBNP levels from ≥ 1600 pg/mL (189 pmol/L) to ≥ 1400 pg/mL (166 pmol/L)	
Section 3.3.1: Inclusion Criteria; Synopsis	Inclusion criteria # 2H) was modified to decrease the minimum allowable body weight from ≥ 50 kg to ≥ 40 kg	
Section 3.3.2: Exclusion Criteria; Synopsis	Exclusion Criteria # 4D) was modified to: Subjects treated with oral phosphodiesterase type 5 (PDE5) inhibitor sildenafil, vardenafil or avanafil within 24 hours of screening or treated with tadalafil within 4 days of screening, oral inotropic agents (eg, pimobendan) or oral vasopressin V2 receptor antagonist (eg, tolvaptan) initiated for the current ADHF episode. NOTE: chronic use of tolvaptan is not exclusionary.	
Section 4.6.2 Other Blinding and Unblinding	Section was modified to include: The second interim analysis will be performed when 210 randomized subjects reach the last visit at Day 32 in Part II (Cohort 2). The study analysis team will then provide top-line results to the project team.	

SUMMARY OF KEY CHANGES FOR REVISED PROTOCOL 02A		
Section Number & Title	Description of Change	Brief Rationale
	
The follow-up to Day 182 for both Part I and Part II will be site-and-subject blinded.
 
Japanese subjects enrolled as part of the 210 subject global cohort (Part II, Cohort 2) will be site-and-subject blinded until the end of the study in Japan.
	
Section 8.1: Sample Size Determination	Section was modified to add: While the enrollment in the main study protocol will continue until 210 patients have been randomized globally in Part II (Cohort 2), enrollment may continue further only in Japan until approximately 18 total Japanese subjects are randomized	
Section 8.4: Analyses	Section was modified to add: Subjects in Japan who started treatment after last patient randomization date of subjects who were enrolled before closure of the 210 subject global enrollment will not be part of the main global Part II Day 32 interim analysis. Details will be provided in the statistical analysis plan	
Section 8.5: Interim Analyses	Section was modified to add: The second interim analysis will be performed when 210 randomized subjects reach the last visit at Day 32 in Part II (Cohort 2) in order to facilitate drug development decisions. The study analysis team will then provide	

SUMMARY OF KEY CHANGES FOR REVISED PROTOCOL 02A		
Section Number & Title	Description of Change	Brief Rationale
	
top-line results to the project team.
 
An additional interim analysis may be performed following completion of the last visit at Day 32 of the last enrolled Japanese subject.
	

Overall Rationale for the Revised Protocol 02, 09-Apr-2018

These changes serve to clarify procedures for Part II Cohort 2 of the study. Part I Cohort 1 of the study is not impacted. Changes include:

SUMMARY OF KEY CHANGES FOR REVISED PROTOCOL 02		
Section Number & Title	Description of Change	
Section 3.3.2 Exclusion Criteria	
Exclusion criteria # 2b was modified to clarify:
 
Suspected acute lung disease (eg, pneumonia or asthma) or severe chronic lung disease (eg, severe chronic obstructive pulmonary disease, pulmonary fibrosis, patients with hypercapnia or requiring home oxygen therapy or chronic oral steroids.)
	

SUMMARY OF KEY CHANGES FOR REVISED PROTOCOL 02

Section Number & Title	Description of Change	Brief Rationale
Section 3.1 Study Design and Duration	Changed to: Study Medication infusion must start within 18 hours of presentation (or 48 hours in Part II Cohort 2 of the trial), with presentation defined as the first dose of diuretic for current episode	
Section 5.1.2 Treatment and In-Hospital Follow-up	Addition of window to collect vital signs within .25 hours of specified time points.	
All	Minor formatting and typographical corrections

2 STUDY DESCRIPTION

2.1 Study Design

This is a multi-center, randomized, placebo-controlled, double-blind study of continuous 48-hour intravenous (IV) infusions of BMS-986231 in hospitalized HFREF subjects with ADHF. The trial was designed to identify the doses of BMS-986231 that are safe and tolerated with regard to clinically relevant hypotension.

The study consists of 2 parts, each with a unique cohort of subjects.

[figure not shown]
Subjects that are randomized in Part I of the study will not be allowed to participate in Part II.

In Part I (Cohort 1) of the study, approximately 100 subjects will be randomized in a 1:1 ratio to placebo or an escalating dose of BMS-986231 (3 µg/kg/min for 4 hours, then 6 µg/kg/min for another 4 hours, then 12 µg/kg/min for the remaining 40 hours).

In Part II (Cohort 2) of the study, the 2 highest planned doses of BMS-986231 in Cohort 1, BMS-986231 6 µg/kg/min and BMS-986231 12 µg/kg/min, will be administered. Approximately 210 subjects will be randomized in a 1:1:1 ratio to one of the 2 active doses of BMS-986231 or placebo. If BMS-986231 12 µg/kg/min is not considered to be a tolerated dose in Part I, then BMS-986231 3 µg/kg/min and BMS-986231 6 µg/kg/min will be evaluated in Part II. In the event that neither 6 µg/kg/min nor 12 µg/kg/min are tolerated, the protocol will require modification.

The study design schematic is presented in Figure 2.1-1 for Part I (Cohort 1) and [Figure 2.1-2](#) for Part II (Cohort 2).

Figure 2.1-1: Study Design Schematic Part I (Cohort 1)

[figure not shown]

^a Every effort should be made to initiate study drug administration promptly after randomization

^b Study Medication infusion must start within 18 hours of presentation, defined as the first dose of diuretic for current episode, but not within 2 hours after an IV bolus dose of intravenous diuretics, or within 2 hours after the initiation or an increase in the dose of an IV diuretic administered by continuous infusion

^c Discharge may occur as per standard medical practice. It is recommended that subjects remain in the hospital for at least 24 hours after the completion of the 48-hour infusion of study drug for safety monitoring

Figure 2.1-2: Study Design Schematic Part II (Cohort 2)

a 3 µg/kg/min if 12 µg/kg/min is not tolerated in Part I

b 6 µg/kg/min if 12 µg/kg/min is not tolerated in Part I

c Every effort should be made to initiate study drug administration promptly after randomization

d Study Medication infusion must start within 18 hours of presentation, defined as the first dose of diuretic for current episode, but not within 2 hours after an IV bolus dose of intravenous diuretics, or within 2 hours after the initiation or an increase in the dose of an IV diuretic administered by continuous infusion

e Discharge may occur as per standard medical practice. It is recommended that subjects remain in the hospital for at least 24 hours after the completion of the 48-hour infusion of study drug for safety monitoring.

Subjects must be randomized and treated within 18 hours of presentation, defined as the first dose of IV diuretic for the current episode of ADHF. In addition, subjects must not be randomized within 2 hours following an IV bolus dose of diuretic, or within 2 hours after the initiation or an increase in the dose of an IV diuretic administered by continuous infusion. It is recommended that subjects remain in the hospital for at least 24 hours after the completion of the 48-hour infusion of study drug for safety monitoring.

Every effort must be made to initiate study drug administration promptly after randomization.

The inpatient period will end in conjunction with the final inpatient assessment at Hour 120 or discharge. All subjects will be followed for safety and rehospitalization endpoints through Day 32 and mortality through Day 182.

The start of the trial is defined as the first subject screened. End of trial is defined as the last Day 182 follow-up visit, or withdrawal date (for subjects who withdraw prematurely from the study) by any patient, whichever comes later.

2.2 Treatment Assignment

At the time of screening for both Part I (Cohort 1) and Part II (Cohort 2), each subject will be assigned a unique sequential subject number by interactive response technology (IRT). The IRT will be available 24 hours per day, 7 days a week. The subject number will consist of a unique 5 digit number which is assigned sequentially within a study (starting with 00001) by the IRT. This number will be used for identification throughout the study and will not be used for any other subject. Subjects screened for Part I, (Cohort 1) will be assigned sequential study numbers beginning with 00001, and subjects screened for Part II, (Cohort 2) will be assigned sequential study numbers beginning with 10001.

Randomization schedules will be generated by BMS and kept by the IRT vendor. Subjects who meets the inclusion/exclusion criteria will be randomly assigned by the IRT to placebo or an incremental dose of BMS-986231 (3 - 6 - 12 µg/kg/min) in a 1:1 ratio for Part I (Cohort 1) and placebo or 1 of the 2 active dose levels of BMS-986231 in a 1:1:1 ratio for Part II (Cohort 2).

Randomization will be stratified by the following regions: North America, Europe, and Latin America (Argentina only).

2.3 Blinding and Unblinding

The Data Monitoring Committee (DMC; see [Section 2.5.1](#)) will assess safety on an ongoing basis, and will have access to unblinded treatment codes for individual subjects. An analysis team, including a reporting statistician and programming support, who are not involved with the conduct of the study, will provide analyses to the DMC.

Two interim analyses will be performed in this study (see [section 7.11](#)).

The first unblinded interim analysis will be performed by the analysis team at the completion of the last visit at Hour 120 in Part I (Cohort 1). This analysis will be reviewed by the DMC and will be reviewed in parallel and by the executive committee (see [Section 2.5](#)) and Sponsor representatives. The rationale for a fully unblinded review by the executive committee and Sponsor is to determine whether 12 µg/kg/min is an appropriate dose to study in Part II.

The second interim analysis will be performed following completion of the last visit at Day 32 in Part II (Cohort 2). The study analysis team will then provide top-line results to the project team.

The follow-up to Day 182 for both Part I and Part II will be site-and-subject blinded.

In certain circumstances a pharmacokineticist or designates in Clinical Pharmacology and Pharmacometrics, biostatisticians and programmers at BMS, or designee, may be unblinded in

order to prepare preliminary summaries of pharmacokinetics (PK) and safety data, as needed. These summaries will not reveal individual subjects' treatment assignments.

2.4 Protocol Amendments

This statistical analysis plan (SAP) is based on the revised protocol version 01 which incorporates Amendment 01, dated 11-Oct-2016.

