3.3.1 Inclusion Criteria

1) Signed Written Informed Consent

- a) Subjects will be required to provide a written informed consent

2) Target Population

- a) Subjects being hospitalized for ADHF
- b) Have had at least 40 mg furosemide intravenous, or equivalent (e.g 40 mg furosemide equivalent to 20 mg torsemide or to 1 mg bumetanide) for the current ADHF episode
- c) Subject must be randomized and treated within 18 hours of first dose of intravenous diuretic for Part I Cohort 1 (or 48 hours of first dose for Part II Cohort 2).
- d) Have dyspnea at rest or with minimal exertion after administration of at least 1 dose of intravenous diuretics. Subject must not be randomized within 2 hours after an IV bolus dose of intravenous diuretics, or within 2 hours after the initiation or a dose increase of an IV diuretic administered by continuous infusion
- e) Have a history of heart failure and a left ventricular ejection fraction (LVEF) $\leq 40\%$, as assessed by echocardiography, a multigated acquisition (MUGA) scan or magnetic resonance imaging (MRI) scan

Note: Ejection fraction documentation up to 18 months prior to screening may be used if there is no clinical expectation of improvement in ejection fraction in that timeframe (eg, the patient has not had biventricular pacing initiated during that period)

- f) Have at least 2 of the following at time of screening:
 - i) evidence for pulmonary congestion on chest x-ray
 - ii) rales by chest auscultation,
 - iii) edema $\geq 2+$ on a 0 to 3+ scale (easily identifiable indentation, skin rebounds in 15-30 seconds)
 - iv) presence of jugular venous distention
- g) Have an elevated NT-proBNP ≥ 1600 pg/mL (189 pmol/L) or BNP ≥ 400 pg/mL (116 pmol/L) as determined at the local laboratory within 18 hours prior to the start of study drug infusion for Part I Cohort 1 (or 48 hours for Part II Cohort 2)

For subjects with atrial fibrillation: NT-proBNP ≥ 2400 pg/ml or BNP ≥ 600 pg/ml

- h) Body weight ≥ 50 kg and < 140 kg at screening
- i) Subject Re-Screening: This study permits the re-screening of a subject that has discontinued the study as a screen failure (has not been randomized). See [Section 5.1.1](#) for more details

3) Age and Reproductive Status

- a) Males and Females, at least age 18 (or age of majority) (Germany only, see [Appendix 3](#))

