3.3.1 Inclusion Criteria

1) Signed Written Informed Consent

- a) Subjects will be required to provide a written informed consent

2) Target Population

- a) Subjects being hospitalized for ADHF
- b) Have had at least 40 mg furosemide intravenous, or equivalent (e.g 40 mg furosemide equivalent to 20 mg torsemide or to 1 mg bumetanide) for the current ADHF episode
- c) Subject must be randomized and treated within 18 hours of first dose of intravenous diuretic for Part I Cohort 1 (or 48 hours of first dose for Part II Cohort 2).
- d) Have dyspnea at rest or with minimal exertion after administration of at least 1 dose of intravenous diuretics. Subject must not be randomized within 2 hours after an IV bolus

dose of intravenous diuretics, or within 2 hours after the initiation or a dose increase of an IV diuretic administered by continuous infusion

- e) Have a history of heart failure and a left ventricular ejection fraction (LVEF) $\leq 40\%$, as assessed by echocardiography, a multigated acquisition (MUGA) scan or magnetic resonance imaging (MRI) scan

Note: Ejection fraction documentation up to 18 months prior to screening may be used if there is no clinical expectation of improvement in ejection fraction in that timeframe (eg, the patient has not had biventricular pacing initiated during that period)

- f) Have at least 2 of the following at time of screening:
 - i) evidence for pulmonary congestion on chest x-ray
 - ii) rales by chest auscultation,
 - iii) edema $\geq 2+$ on a 0 to 3+ scale (easily identifiable indentation, skin rebounds in 15-30 seconds)
 - iv) presence of jugular venous distention
- g) Have an elevated NT-proBNP ≥ 1400 pg/mL (166 pmol/L) or BNP ≥ 350 pg/mL (101 pmol/L) as determined at the local laboratory within 18 hours prior to the start of study drug infusion for Part I Cohort 1 (or 48 hours for Part II Cohort 2)
For subjects with atrial fibrillation: NT-proBNP ≥ 2400 pg/ml or BNP ≥ 600 pg/ml
- h) Body weight ≥ 40 kg and < 140 kg at screening
- i) Subject Re-Screening: This study permits the re-screening of a subject that has discontinued the study as a screen failure (has not been randomized). See [Section 5.1.1](#) for more details

3) Age and Reproductive Status

- a) Males and Females, at least age 18 (or age of majority) (Germany only, see Appendix 3)

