6 STUDY PERIODS, TREATMENT REGIMENS AND POPULATIONS FOR ANALYSES

6.1 Study Periods

Screening period starts from 18 hours prior to start of study drug infusion to Hour 0 (the start of study drug infusion). In-hospital follow-up starts from the end of study drug infusion to Hour 120 or discharge, whichever comes first. Day 32 follow-up occurs 32 days after the start of study drug infusion. Day 182 follow-up occurs 182 days after the start of study drug infusion.

Please see the study design ([Section 2.1](#)) for the details on study periods.

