7.2 Study Conduct

Protocol deviations identified as significant will be captured in a trial management system and reported in the CSR. Relevant protocol deviations are those that are programmable and could potentially affect the interpretability of the study results. The following protocol deviations will be defined as relevant protocol deviations and listed:

- Error in treatment assignment resulting in a subject being dosed with an incorrect treatment
- Subject not treated within 24 hours of first dose of intravenous diuretic (the time difference between start of infusion and first dose of intravenous diuretic > 24 hours)
- Systolic blood pressure (SBP) < 105 mm Hg at screening or Hour 0
- Violation of inclusion criterion 2 (b): Subjects not hospitalized for ADHF
- Violation of inclusion criterion 2 (g): Not having at least 2 of the following at time of screening:
 - i) evidence for pulmonary congestion on chest x-ray
 - ii) rales by chest auscultation,
 - iii) edema $\geq 2+$ on a 0 to 3+ scale (easily identifiable indentation, skin rebounds in 15-30 seconds)
 - iv) presence of jugular venous distention
- Violation of inclusion criterion 2 (h): Have no elevated NT-proBNP ≥ 1600 pg/mL (516 pmol/L) or BNP ≥ 400 pg/mL (116 pmol/L) as determined at the local laboratory within 18 hours prior to the start of study drug infusion. For subjects with atrial fibrillation: no NT-proBNP ≥ 2400 pg/ml or BNP ≥ 600 pg/ml

- Violation of exclusion criterion 4 (a): Subjects administered IV or transdermal nitrate therapy prior to randomization, when at least one of the following criteria are not met:
 - i) Systolic blood pressure at screening or just prior to randomization is > 120 mm Hg
AND
 - ii) The IV nitroglycerin dose is < 100 µg/min (or isosorbide dinitrate < 3 mg/hour), AND
 - iii) The infusion rate and dose has been unchanged for > 2 hours
- Violation of exclusion criterion 4 (d): Subjects treated with oral phosphodiesterase type 5 (PDE5) inhibitor sildenafil, vardenafil or avanafil within 24 hours of screening or treated with tadalafil within 4 days prior to the start of screening
- Initiation of PDE5 inhibitors during study drug infusion

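### The visible SAP follows Revised Protocol 01 and conflicts with later protocols on Part II deviation windows, Japan-extension subjects in the Day 182 tables, and the region list

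*SAP*

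**What the plan says.** **Basis.** SAP 2.4: "This statistical analysis plan (SAP) is based on the revised protocol version 01 which incorporates Amendment 01, dated 11-Oct-2016". The supplied protocol file holds Revised Protocol 02 (April 2018) and Revised Protocol 02c (September 2019), both later.

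**Windows.** SAP 2.1 says "Subjects must be randomized and treated within 18 hours of presentation, defined as the first dose of IV diuretic", with no separate rule for Part II. SAP 6.1 says "Screening period starts from 18 hours prior to start of study drug infusion to Hour 0". SAP 7.2 lists as a relevant deviation "Subject not treated within 24 hours of first dose of intravenous diuretic", and also a natriuretic peptide that does not reach 1600 pg/mL (NT-proBNP) or 400 pg/mL (BNP) within 18 hours before infusion. Section 3.3.1 of both protocols keeps 18 hours for Part I but adds, for treatment, "or 48 hours of first dose for Part II Cohort 2", and for the peptide, "within 18 hours prior to the start of study drug infusion for Part I Cohort 1 (or 48 hours for Part II Cohort 2". Version 02c also lowers the peptide threshold: "Have an elevated NT-proBNP ≥ 1400 pg/mL (166 pmol/L". Appendix 3 introduces the 02a changes, which include this one, as follows: "These changes serve to clarify the milestone, timing of enrollment and inclusion/exclusion criteria of the Japanese population".

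**Population.** SAP 6.3 puts every infused subject in the Treated set. SAP 7.6.1 divides events by all subjects treated, and SAP 7.6.2.1 handles Day 182 deaths the same way. SAP 7.3.1 tabulates completion of the Day 182 phase for all treated subjects. Protocol 02c section 8.4 removes subjects treated in Japan after the global cut-off from the main Part II Day 32 and Day 182 analyses and leaves the details to the SAP. Sections 3.1 and 5.7.3 follow them to Day 32 only.

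**Region.** SAP 2.2 and Table 7.3-1 list North America, Europe and Latin America. Protocol 02c sections 1.3.4 and 4.6.2 refer to Japanese subjects inside the global 210. SAP 7.5.2 puts region and time-by-region in the dyspnea NRS model.

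**The concern.** A SAP that trails the protocol is harmless where the protocol settles the matter alone. Here the SAP contains working rules that give the wrong output if followed.

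SAP 7.2 reserves the label of relevant deviation for departures that could bear on how the results are interpreted. Applying it to Part II subjects who met their own eligibility window would misreport trial conduct.

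The protocol hands the details of the Japan exclusion to the SAP, and the visible SAP does not mention Japan. A programmer working from it would keep extension subjects in the Day 182 denominator without having observed them after Day 32.

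The dyspnea model needs a region level that the SAP does not define for some main-analysis subjects. If these choices are made after Part II is unblinded, they become post hoc.

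**Working it through.** **1. Windows, side by side**

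| Item | SAP | Protocol 02 and 02c, Part II |
|---|---|---|
| First IV diuretic to infusion | listed if > 24 h (7.2); 18 h (2.1) | 48 h |
| Peptide before infusion | 18 h (7.2) | 48 h |
| Screening period | 18 h (6.1) | 48 h (Table 5.1-1) |
| NT-proBNP threshold | 1600 pg/mL | 1600 (02), 1400 (02c) |

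A Part II subject infused at hour 30 meets the protocol and is listed by the SAP. The 24-hour limit can be read as a tolerance around the 18-hour criterion, but not around 48 hours. The part of the permitted window that triggers a listing is (48 − 24)/48 = 50% for treatment and (48 − 18)/48 = 62.5% for the peptide. These are shares of time, not of subjects. The number of subjects affected is not given; for scale only, an assumed 10% of 210 is 21 and an assumed 50% is 105. SAP 6.3 defines no per-protocol set, so a listed subject stays in every analysis.

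The 1600 pg/mL rule would also list non-atrial-fibrillation subjects who qualified on NT-proBNP at 1400–1599 pg/mL where versions 02a–02c applied.

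**2. Extension subjects**

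Inputs: 70 per group × 3 = 210 for global Part II, and about 18 Japanese subjects in total (Protocol 02c section 8.1). Let k be the Japanese subjects inside the 210. The documents do not give k. The extension is then 18 − k and the literal SAP denominator is 210 + 18 − k = 228 − k.

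- Extension share = (18 − k)/(228 − k)
- Day 182 dilution factor = 210/(228 − k), assuming equal allocation and no recorded extension deaths

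| k (assumed) | Extension share | Factor | 10.0% true rate appears as |
|---|---|---|---|
| 0 (bound) | 18/228 = 7.9% | 0.921 | 9.2% |
| 6 | 12/222 = 5.4% | 0.946 | 9.5% |
| 9 | 9/219 = 4.1% | 0.959 | 9.6% |
| 18 (bound) | 0 | 1.000 | 10.0% |

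The relative risk is unchanged under these assumptions; a risk difference shrinks by the same factor. If half of all deaths fell by Day 32 (assumed), the factor is (210 + 0.5(18 − k))/(228 − k): 0.973 at k = 6 and 0.979 at k = 9.

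For the hypotension endpoint, follow-up is complete and there is no expected change if extension subjects have the same rate. At k = 9, three subjects are added per arm, and 7/70 = 10.0% becomes 7/73 = 9.6% or 8/73 = 11.0% with no or one added event.

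If section 8.4 is applied, the denominator is 210 and all of these effects vanish.

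**3. Region**

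Subjects with no listed level are k/210: 6/210 = 2.9% at k = 6 and 9/210 = 4.3% at k = 9. They must be given a level, merged into another, or lost from the model. SAP 7.6.1 uses no region term.

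**4. Units**

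SAP 7.2 prints 1600 pg/mL as 516 pmol/L; Protocol 02 section 3.3.1 prints 189. The ratios are 516/1600 = 0.32 and 189/1600 = 0.118, and 02c's 166/1400 = 0.119 agrees with the second.

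**The case against.** The SAP declares its base version, and the 48-hour window and the Japan rules came later. Section 8.4 speaks of SAP details still to come, and parts of the posted SAP are removed or redacted. The documents therefore show which SAP was posted, not which one governed the Part II analysis. This stands, and it is why the point concerns the visible SAP only.

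Section 8.4 itself states the exclusion, so the dilution figures describe an analysis that the protocol rules out. This also stands: they are bounds on a literal reading of the SAP. The two ends of the range are unlikely, because the protocol refers to Japanese subjects both inside the 210 and after closure. The gap that remains is the missing rule that the protocol assigns to the SAP.

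Randomization is stratified by region, so Japanese subjects should already carry a stratum. That makes the repair easy, but the SAP's list still omits it.

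A reader might infer several stronger points that the documents do not support:

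- **That Day 182 denominators misfit all Japanese subjects.** Those inside the 210 are followed to Day 182 and fit.
- **That the deviation rules bias a result.** No analysis set depends on them.
- **That the SAP's inclusion-criterion letters are wrong.** They differ from both supplied protocols but may match Revised Protocol 01, which is not supplied.
- **That the second-interim trigger in SAP 7.11 is a separate error.** It matches section 8.5 of Revised Protocol 02 and differs only from 02c.

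**Conclusion.** The point holds as a misalignment of the visible SAP with the supplied protocols, at medium confidence. It should be corrected, but it does not threaten the primary result.

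- **Deviations:** protocol-compliant Part II subjects would be reported as relevant deviations. The number is unknown and no estimate changes.
- **Day 182:** read literally, extension subjects alive at Day 32 count as Day 182 non-deaths and have no Day 182 phase to complete. They are fewer than about 18 and under about 8% of the treated set. The effect is nil once section 8.4 is applied.
- **Region:** an unspecified level affects a secondary model only.

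The sizes rest on about 18 Japanese subjects in total, an unstated split between the global cohort and the extension, and equal allocation. The pmol/L discrepancy is clerical, since the pg/mL threshold in SAP 7.2 agrees with Revised Protocol 02.

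**What to change.** Amend the SAP before the Part II Day 32 analysis:

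- **Population:** restrict the main Part II data sets, including Day 182 mortality and Day 182 disposition, by the section 8.4 cut-off. Report the Japan extension separately through Day 32.
- **Region:** extend the list to cover Japanese subjects, using the stratum as randomised, with a stated rule if that level is too sparse for the time-by-region term.
- **Deviations:** apply windows and peptide thresholds by Part and by the protocol version under which each subject enrolled. The sponsor must reconcile the 18, 24 and 48 hour passages; no view is taken here on which window is right.
- **Housekeeping:** reconcile 516 with 189 pmol/L for 1600 pg/mL.

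The cost is one SAP amendment and the matching programming changes. No new data are needed.
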